AST	aspartate aminotransferase
AUC	area under the time-concentration curve
AV	atrioventricular
BMI	body mass index
BSA	body surface area
CHF	chronic heart failure
Cmax	maximum drug concentration in plasma
CO	cardiac output
CRF	case report form
CV	cardiovascular
DMC	Data Monitoring Committee
e.g.	for example (exempli gratia)
ECG	electrocardiogram
eCRF	electronic CRF
EF	ejection fraction
eGFR	estimated glomerular filtration rate
EQ-5D-5L	EuroQol Group 5-dimensional, 5-level questionnaire
EU	European Union
EWDT	E-wave deceleration time
FAS	full analysis set
GFR	glomerular filtration rate
GGT	gamma glutamyl transpeptidase
HDL	high-density lipoprotein
HF	heart failure
HFpEF	heart failure with preserved ejection fraction
HR	heart rate
hs-TNT	high sensitivity troponin T
i.e.	that is (id est)
ICH	International Conference on Harmonization
INR	international normalized ratio
ITT	intent-to-treat
IVSD	interventricular septum diameter
KCCQ	Kansas City cardiomyopathy questionnaire
LA	left atrial

Statistical Analysis Plan

Protocol No.: < BAY 1067197/17582 >

Page: 6 of 38

LAV	LA volume
LAVI	LA volume index
LDH	lactate dehydrogenase
LDL	low-density lipoprotein
LV	left ventricular
LVEDV	LV end-diastolic volume
LVEDVI	LVEDV index
LVEF	left ventricular ejection fraction
LVESV	left ventricular end-systolic volume
LVESVI	LVESV index
MAP	mean arterial pressure
MCH	mean corpuscular hemoglobin
MCHC	MCH concentration
MCP	multiple comparison procedures
MCV	mean corpuscular volume
MedDRA	Medical Dictionary for Regulatory Activities
mL	milliliter
MRA	mineralocorticoid receptor antagonist
NGAL	neutrophil gelatinase-associated lipocalin
NONMEM	non-linear mixed effect modeling
NT-proBNP	N-terminal pro-hormone b-type natriuretic peptide
NYHA	New York Heart Association
PASP	pulmonary artery systolic pressure
Pes	end-systolic pressure
pg	picogram
PK	pharmacokinetic
PKS	PK analysis set
PP	pulse pressure
PPS	per-protocol set
PTT	partial thromboplastin time
PWT	posterior wall thickness
RV	right ventricular
SAC	systemic arterial compliance
SAE(s)	serious adverse event(s)
SAF	safety analysis set
SAP	statistical analysis plan
SBP	systolic blood pressure
SV	stroke volume
SVI	SV index
TAPSE	tricuspid annular plane systolic excursion

Statistical Analysis Plan

Protocol No.: < **BAY 1067197/17582** >

Page: 7 of 38

TD	Tissue Doppler
TPR	total peripheral resistance
UACR	urine albumin-to-creatinine ratio
WOV	worst observation value

Statistical Analysis Plan

Protocol No.: < BAY 1067197/17582 >

Page: 8 of 38

1. Introduction

This statistical analysis plan (SAP) describes the study objectives, study design, study population, efficacy and safety variables, statistical analysis methods, and study tables to be used in this study. It is based on the original protocol, Version 1.0, dated 14 FEB 2017.

2. Study Objectives

[figure not shown]
The objective of the study is to find the optimal dose of neladenoson bialanate for the Phase III trial by detecting and characterizing a significant dose-response relationship in the primary efficacy endpoint, absolute change from baseline in 6-minute walking distance (6MWD) at 20 weeks, in patients with chronic heart failure with preserved ejection fraction (HFpEF), and by characterizing the safety, tolerability and pharmacodynamic effects of the compound when given in addition to appropriate therapy for specific co-morbidities.

An exploratory objective is to further assess pharmacokinetic parameters and blood and urine biomarkers.

3. Study Design

Study 17582 is a multicenter, randomized, placebo-controlled, parallel group, double blind, dose-finding Phase II study. [Figure 3-1](#) displays the overall study design.

Figure 3-1: Study design overview

Abbreviations: CV = cardiovascular; ICF = informed consent form; W = week

Approximately 288 patients from approximately 90 study centers worldwide will be randomized to one of the active treatment dose arms or placebo, in addition to their background therapy.

Statistical Analysis Plan

Protocol No.: < BAY 1067197/17582 >

Page: 9 of 38

The study will comprise a 1-week run-in period, 20-week treatment period, and a 6-week follow-up period (27 weeks total).

Patients will have site visits at Weeks -1, 0 (baseline), 4, 8, 12, 20 (end of treatment visit) and 24 (safety follow-up visit). In addition, 2 phone calls at Weeks 2 and 26 will be made to assess patients' safety, and one additional phone call – to remind the patients of AVIVO self-application at Week 19.

6MWD test (including Borg CR 10 Scale) will be done during the run-in, to familiarize patients with the test, and at baseline, Week 8 and end of treatment / premature discontinuation visits. Safety will be monitored throughout the study. PK samples will be taken from all patients at dedicated time points. Biomarkers reflecting the pharmacodynamic activity of the drug will be examined, as well as candidate biomarkers that may predict drug response.

The anticipated duration of the study as a whole is approximately 19 months: this includes an anticipated recruitment period of 13 months followed by a run-in period of 1 week, a treatment period of 20 weeks and a follow-up period of 6 weeks after enrollment of the last patient into the trial.

A parallel group design was chosen to compare five different once-daily dose regimens and one placebo arm to find the best dose for Phase III. Placebo control is used to control for observer and subject bias, and randomization - to control for assignment bias. The dose range around 20 mg (5, 10, 30 and 40 mg) is to ensure different data points to feed the MCP mod predefined models and potential unforeseen variances. The doses studied will ensure a strong dose recommendation moving forward into phase III. Safety of the subjects in this parallel study design will be closely monitored by a Data Monitoring Committee (DMC).

The end of the study as a whole will be reached as soon as the last visit of the last patient has occurred in all centers in all participating countries (EU and non-EU).

4. General Statistical Considerations

4.1 General Principles

The statistical evaluation will be performed by using the software package SAS version 9.2 or higher (SAS Institute Inc., Cary, NC, USA). Unless otherwise noted, data will be analyzed by descriptive statistical methods: The number of data available and missing data, mean, standard deviation, minimum, quartiles, median, and maximum will be calculated for metric data. Frequency tables will be generated for categorical data.

4.2 Handling of Dropouts

A “dropout” is defined as a patient who has been randomized and discontinues study participation prematurely for any reason, whether or not any study medication was taken. Randomized patients who drop out or withdraw prematurely will not be replaced. Refer to Section 6.4 in the study protocol for withdrawal of patients from study.

Statistical Analysis Plan

See following sections for more details on deriving efficacy endpoints in case of missing data.

4.3 Handling of Missing Data

Generally, missing data will be handled as such, i.e., no imputation of missing data will be performed. An exception is the analysis of the primary and secondary efficacy variables, and the timing of events relative to other events.

All missing or partial data will be presented in the patient data listing as they are recorded in the eCRF.

A number of descriptive analyses will be performed to better understand missing data patterns. The frequency, proportion and the reasons for premature discontinuation of both the study and study treatment will be reported. Kaplan-Meier plots for “time to end of study treatment (calculated as days from first dose to the earliest date of stop medication, including premature stop of study medication and death, for the calculation all the subjects will be considered to have an event, i.e. stop of study medication)” and “time to end of study” (calculated from randomization to the earliest date of visit 9, death, and the last visit if subject drops off from study prematurely, for the calculation all the subjects will be considered to have an event, i.e. stop of study) will be provided, by treatment group and overall.

The number of patients who prematurely discontinue study participation or intake of study medication and the corresponding reasons will be summarized with respect to the key subgroups (see Section 4.5.4). If the proportion of patients who withdraw across the dose groups is not fairly balanced, the impact on the primary variables will be further explored. To further explore the missingness pattern with regards to the “missing at random” assumption, the mean of the baseline values of the efficacy variable will be summarized for patients with and without post-baseline observations, by treatment group and overall.

For the analysis of the primary and secondary variables, it cannot necessarily be assumed that data are missing at random. As the choice of primary analysis will be based on assumptions that cannot be verified, the robustness of the results of the primary analysis will be investigated through appropriate sensitivity analyses making different assumptions, in accordance with the EMA “Guideline on missing data in confirmatory clinical trials”. Detail missing data handling are specified in Section 6.2.1.4.

When appropriate, the following rules will be implemented so as not to exclude subjects from statistical analyses due to missing or incomplete data:

- Date of chronic heart failure (CHF) diagnosis

For cases where start month and year are reported but day is missing, impute it with 01.month.year. If the month is not available, this date will not be imputed.

- Clinical outcomes

For cases where start month and year are reported but day is missing, impute the maximum of (date of randomization, first date of study medication, 15.month.year). For cases where only start year is reported or completely missing, impute the maximum of (date of randomization, first date of study medication, 15.01.year), but not later than death date if the subject died.

Statistical Analysis Plan

Protocol No.: < BAY 1067197/17582>

Page: 11 of 38

- Heart failure (HF) related concomitant medication start date

For case where start month and year are reported but day is missing, impute it with 15th day of month. For cases where only start year is reported or completely missing, impute it as maximum of (15.01.year, date of randomization).

- HF related concomitant medication stop date

For case where stop month and year are reported but day is missing, impute it as minimum of [(15, month, year) and (last visit date) and (death date)].

If the stop day and month are missing, then the stop date will be imputed as minimum of [(15.12.year) and (last visit date) and (death date)].

If the date is completely missing then the stop date will be imputed as minimum of [the last visit date and death date]. If the concomitant medication is “Ongoing at subject's last visit”, for the respective stop date variable the ‘last visit date’ from the corresponding domain is merged in the concomitant medication database by data management programming.

- Study medication start date

If the start date and time is missing it will be imputed with the randomization date and time. If start date and time is recorded as earlier than randomization and cannot be clarified, date and time of randomization will be used for the statistical analysis.

- Study medication stop date

If the stop day is missing, but the stop month and stop year are available then the stop date will be imputed as minimum of [(15, month, year) and (last on-treatment visit date) and (death date)].

If the stop day and month are missing or the date is completely missing then the stop date will be imputed as minimum of [(last on-treatment visit date) and (death date)].

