6.2.3 Exploratory efficacy variables and analyses

Exploratory efficacy variables include:

- Echocardiographic parameters, as described in Section 9.4.3 of Clinical Study Protocol, measured values and absolute / relative change from baseline at 20 weeks
- Mandatory biomarkers, as described in Section 9.4.4 of Clinical Study Protocol, measured values and absolute / relative change from baseline at 20 weeks, including UACR, cystatin-C, NGAL for the evaluation of kidney function
- Time from randomization to CV mortality, HF hospitalization and urgent visits for HF as clinical outcomes (both separate and composite outcomes)
- Time from randomization to all-cause mortality, non-fatal myocardial infarction, non-fatal stroke
- EQ-5D-5L QoL, as described in Section 9.4.6.2 of Clinical Study Protocol, measured values and absolute / relative change from baseline
- KCCQ (Appendix 9.3; excluding symptom stability domain and self-efficacy domain), measured values, absolute change and relative change from baseline
- Change in NYHA class
- Absolute change in score on Borg CR 10 Scale

Time to adjudicated clinical outcome events since randomization (both separate and composite outcomes) will be described by means of Kaplan-Meier estimates by visit in FAS. The subjects who do not have the corresponding clinical outcomes until week 26 (planned Visit 9, upper time limit, i.e. $182+7=189$ days) will be considered as right-censored at the minimum of date of last visit, date of Visit 9, and date of death (in case death is non CV death). KM estimates will be presented by individual treatment groups and by all neladenoson groups pooled as well as 5 mg and 10 mg doses pooled as low dose, 20 mg, 30 mg, 40 mg doses pooled as high dose versus placebo.

Additionally time to adjudicated on-treatment clinical outcome events since randomization (using both separate and composite outcomes) will also be described by means KM estimates

Statistical Analysis Plan

by visit. The subjects who don't have the corresponding clinical outcomes 6 weeks after last dose will be considered right censored at minimum of date of last visit, 6 weeks after last dose and date of death (in case death is non CV death). KM estimates will be presented by individual treatment groups and by all neladenoson groups pooled as well as 5 mg and 10 mg doses pooled as low dose, 20 mg, 30 mg, 40 mg doses pooled as high dose versus placebo.

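### SAP 4.3: an outcome event of known month has no death-date cap, and undated or same-year year-only events are placed at day 0

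*SAP*

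**What the plan says.** SAP 4.3 (Handling of Missing Data, Clinical outcomes) has two sentences.

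- **Month and year known, day missing:** "impute the maximum of (date of randomization, first date of study medication, 15.month.year", and nothing after it. No upper limit is given.
- **Only the year known, or nothing known:** "impute the maximum of (date of randomization, first date of study medication, 15.01.year), but not later than death date if the subject died".

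The same section treats stop dates differently. For an HF-related concomitant medication with a known stop month the rule is "impute it as minimum of [(15, month, year) and (last visit date) and (death date". The study-medication stop date with a known month is likewise limited by the last on-treatment visit and by death.

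The dates are used in SAP 6.2.3: "Time to adjudicated clinical outcome events since randomization (both separate and composite outcomes) will be described by means of Kaplan-Meier estimates by visit in FAS". A second, on-treatment version follows events to 6 weeks after the last dose. Patients without the event "will be considered as right-censored at the minimum of date of last visit, date of Visit 9, and date of death" (the last when the death is not cardiovascular), so censoring times have upper bounds.

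**The concern.** There are two separate weaknesses.

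First, the known-month rule can produce an impossible sequence: a hospitalisation, infarction or stroke dated after the patient died. In a composite with CV death, the death would then be counted first, although the hospitalisation came first. The cap that prevents this stands in the very next sentence and in the stop-date rules, so its absence looks like an omission.

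Second, the rule for year-only and undated events leans early. It takes the earliest candidate in the calendar year and then raises it to randomisation or first dose. Many such events therefore sit at the origin of the curve. A day-0 event in a treated patient is also automatically on-treatment, even if it really occurred more than 6 weeks after study drug was stopped.

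**Working it through.** The plan gives no figure for this rule, so there is nothing to reproduce. The two sentences were applied as written.

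**Inputs from the documents**
- The two date rules and the stop-date rules: SAP 4.3.
- Follow-up: 182 days, or 189 at the "planned Visit 9, upper time limit" (SAP 6.2.3).
- Recruitment: "anticipated recruitment period of 13 months" (SAP 3), taken as 395 days.
- First dose taken at the randomisation visit: Protocol 9.2.2. First dose is therefore set to day 0.

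**Assumptions not in the documents**
- Recruitment uniform over the 395 days, with the start month varied from January to December 2017.
- Event day uniform on 1–182 or 1–189.

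**1. Known month.** Imputed date = max(randomisation, first dose, 15th of the month). If the patient dies on day d of that month and d ≤ 14, the 15th is 15 − d days after death, which is 1 to 14 days. Example: randomised 1 September 2017, hospitalisation known only as March 2018, death on 6 March 2018. The rule gives 15 March, 15 − 6 = 9 days after death.

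How often this happens, given an event and a death in the same month of M days:
- Death day uniform: 14/M, which is 14/31 = 45% to 14/28 = 50%.
- All ordered pairs with the event on or before the death equally likely: (1 + 2 + … + 14) / (M(M + 1)/2) = 105/496 = 21% (M = 31) to 105/406 = 26% (M = 28).

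The second version respects the order of events and is the more relevant one.

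**2. No date at all.** There is no year, so 15 January cannot be formed. Only randomisation and first dose remain, and the result is always day 0. With a uniform event day on 1–182 the mean shift is (1 + 182)/2 = 91.5 days, about 13 weeks early.

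**3. Year only.** Imputed date = max(randomisation, first dose, 15 January of that year), capped at death.
- Event in the calendar year of randomisation: 15 January is on or before randomisation unless the patient was randomised on 1–14 January, so the result is day 0. Example: randomised 1 September 2017, true event 10 December 2017 (day 100), imputed day 0.
- Event in the following calendar year: 15 January of that year. Example: same patient, true event 20 February 2018 (day 172), imputed day 136.

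Enumerating every randomisation day and event day over all start months and both follow-up lengths:

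| Result for year-only events | Range |
|---|---|
| Placed at day 0 | 65–73% |
| Event in the following calendar year, so 15 January | 23–31% |
| Mean shift, imputed minus true | 70–76 days early |

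The remainder are same-year events of patients randomised on 1–14 January, also moved to 15 January.

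**4. On-treatment status.** For a patient who completes treatment, 20 + 6 = 26 weeks, which is essentially the whole follow-up, so the imputed date hardly matters. It matters for a patient who stops early and has the event more than 6 weeks after the last dose. An imputed day 0 then puts that event on-treatment.

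**The case against.** The strongest case is that this will rarely matter.

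- Deaths and inpatient hospitalisations are generally serious adverse events, reportable within 24 hours (Protocol 9.6.1.1 and 9.6.1.4). Suspected endpoints must be sent for adjudication, and missing documentation is queried (Protocol 9.4.5.1). The adjudication charter, which is not among the documents, may already assign dates.
- The displays are exploratory and descriptive, without type I error control (Protocol 10.3.2). The primary 6MWD analysis uses whether a CV death or HF hospitalisation prevented the Week 20 assessment, not an imputed date.
- Kaplan-Meier estimates are reported by visit, and visits are 2 to 8 weeks apart, so a shift of at most two weeks will seldom change a reported value.
- Any imputed date is arbitrary, and early dating at least keeps the event in the on-treatment analysis.

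Most of this stands and keeps the point minor. It does not remove it. Protocol 9.4.5.1 and 13.1 do not say that adjudication supplies missing dates, and the SAP provides a rule because it allows for some. By-visit reporting softens the missing cap, but not a shift of 10 to 11 weeks to the origin.

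Three stronger readings are tempting and not supported:
- *A reader might infer that every year-only event goes to randomisation.* It does not: those in the following calendar year go to 15 January.
- *A reader might infer that both sentences allow dates after death.* Only the known-month sentence does; the other has the cap.
- *A reader might take one event in an arm of 24 to 72 patients (1/72 = 1.4 to 1/24 = 4.2 percentage points) as the error in the curve.* The event is real and produces about that step at its true date as well. With complete follow-up the estimate at the end is unchanged; only the timing of the step is wrong.

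**Conclusion.** The point holds, as a minor one with two parts.

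- **Known month:** the missing cap follows from the text alone. It can date a non-fatal event up to 14 days after death and disagrees with the neighbouring rules. Where event and death share a month, this would affect about 21–26% of cases if both days are uniform with the event no later than the death, or 45–50% if only the death day is taken as uniform.
- **Year-only and undated:** undated events always go to day 0. That 65–73% of year-only events do so, and that the mean shift is 70–76 days early, rests on uniform recruitment and uniform event times.

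These are conditional figures. The documents give no rate of partial or missing dates, so the number of patients affected cannot be stated. The consequence is confined to the exploratory displays of SAP 6.2.3, with possible on-treatment misclassification only for early discontinuers. The dose-response conclusion on 6MWD does not depend on it.

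**What to change.** In SAP 4.3, Clinical outcomes:

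1. Extend the known-month rule so that the imputed date is no later than the death date or the last contact. In the March 2018 example this gives 6 March instead of 15 March.
2. For year-only and undated events, impute within the feasible window. It runs from the later of randomisation and the start of the known period to the earliest of the end of that period, death and last contact. The midpoint is a simple choice. For the patient randomised on 1 September 2017 with an event known only as 2017, the window is 1 September to 31 December and the midpoint is about day 60, against day 0 now and a true day of 100.
3. Where the Clinical Events Committee has assigned a date, use that first.

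The cost is a few lines of SAP text and code. No new data are needed.

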 (e.g. social hospitalization for purposes of respite care).

However, it should be noted that invasive treatment during any hospitalization may fulfill the criterion of 'medically important' and as such may be reportable as an SAE dependent on clinical judgment. In addition, where local regulatory authorities specifically require a more stringent definition, the local regulation takes precedence.

- d. Results in persistent or significant disability / incapacity
 Disability means a substantial disruption of a person's ability to conduct normal life's functions.
- e. Is a congenital anomaly / birth defect
- f. Is another serious or important medical event as judged by the investigator

Definition of treatment-emergent adverse event

An AE is classified as treatment-emergent if it occurs or worsens after the first dose of study drug up to 6 weeks after the last dose of study drug.

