6.3.1 Extent of exposure

Study medication will be summarized for the safety population by treatment group, using descriptive statistics such as frequency and proportion (for categorical variables), mean, median, and standard deviation (for continuous variables).

The treatment duration (date of last study medication- date of first study medication+1) will be summarized descriptively. Additionally the number of subjects by treatment duration category will be given (≤ 28 days, $>28-\leq 56$ days, $>56-\leq 84$ days, $>84-\leq 140$ days).

The time on study medication (treatment duration excluding days off study medication) will be calculated and summarized descriptively.

The number of tablets taken will be summarized descriptively, as well as corresponding extent of exposure (total amount of intake in mg).

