6.3.4 Adverse events

All adverse events (AEs) will be coded according to the Medical Dictionary for Regulatory Activities (MedDRA) in its latest version which is specified in the TS domain.

A treatment-emergent AE is defined as any event arising or worsening after the start of study drug administration until 6 weeks after the last study medication intake.

Summary statistics (frequency and percentage of subjects) will be presented by treatment group using MedDRA for the following:

- Incidence rate of treatment-emergent AEs.
- Incidence rate of drug-related treatment-emergent AEs.
- Incidence rate of treatment-emergent AEs leading to death.
- Incidence rate of treatment-emergent AEs leading to permanent withdrawal of medication.
- Incidence rate of treatment-emergent AEs leading to interruption of medication.
- Incidence rate of treatment-emergent serious adverse events (SAEs).
- Incidence rate of treatment-emergent drug-related SAEs.
- Incidence rate of adverse events of special interest:
 - Symptomatic bradycardia (HR < 50 bpm)
 - Findings in ECG and / or AVIVO device as follows:
 - Mobitz type I AV block leading to withdrawal or interruption of study drug
 - Mobitz type II AV block leading to withdrawal or interruption of study drug or leading to any change in therapy
 - Third degree AV blocks

Statistical Analysis Plan

Listing of treatment-emergent AEs leading to withdrawal: subject ID, investigator AE term, primary SOC / preferred term, start and stop date of study drug administration, start and stop date (relative days) of AE, treatment arm, related to study drug / protocol-required procedure (yes/no), serious (yes/no), intensity, outcome.

Listing of treatment-emergent SAEs: subject ID, investigator AE term, primary SOC / preferred term, worst grade, start and stop dates of study treatment, start and stop date of AE , treatment arm, drug related (yes/no), intensity, outcome, action taken.

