6.3.5 Deaths

Deaths reported during the study period will be tabulated by treatment group.

- Summary table of deaths (all deaths, all deaths during treatment and up to 6 weeks after last dose of study drug, all deaths later than 6 weeks after last dose of study medication)
- Listing of subjects who died during treatment and up to 6 weeks after last dose: subject ID, start and stop date of study medication, date of death, and cause of death.

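### The study-drug stop-date rule uses the last on-treatment visit as a ceiling and sets no floor, so a stop date with a missing day can be imputed too early, sometimes before the recorded month or the first dose

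*SAP*

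**What the plan says.** SAP 4.3 has two rules for an incomplete study-medication stop date. With only the day missing, "the stop date will be imputed as minimum of [(15, month, year) and (last on-treatment visit date) and (death date" applies. With day and month missing, or no date at all, the stop date is "imputed as minimum of [(last on-treatment visit date) and (death date". The SAP does not define the last on-treatment visit.

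Two neighbouring rules in SAP 4.3 are built differently. For the stop of a heart-failure medication the plan says to "impute it as minimum of [(15, month, year) and (last visit date) and (death date", which uses the last visit of any kind. For clinical outcomes with a missing day it takes a maximum that includes randomization and first dose, so those dates have a floor.

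The stop date is then used in several places. SAP 6.3.1 states: "The treatment duration (date of last study medication- date of first study medication+1) will be summarized descriptively". SAP 6.3.4 counts as treatment-emergent "any event arising or worsening after the start of study drug administration until 6 weeks after the last study medication intake", and Protocol 9.6.1.1 uses the same 6-week limit. SAP 6.3.5 separates "all deaths during treatment and up to 6 weeks after last dose of study drug" from later deaths. SAP 6.2.3 censors on-treatment clinical outcomes by reference to 6 weeks after last dose, and SAP 4.3 plots time to end of study treatment.

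**The concern.** A patient who is on drug at a visit cannot have stopped before it, so that visit bounds the stop date from below. Placing it inside a minimum makes it a bound from above. The result can contradict what the site recorded: a stop reported for March can be imputed to January. The heart-failure medication rule has the same form, but there the last visit is a sensible upper limit. Replacing it with the last on-treatment visit reverses the meaning of that term.

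On the natural reading, the error runs one way. The imputed date is never later than the true one, so exposure is understated and the 6-week windows for adverse events, deaths and on-treatment outcomes close early. The compliance denominator in SAP 6.3.2 would shrink too, if its actual treatment days are taken from this date. Characterizing safety and tolerability is part of the stated objective.

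**Working it through.** The plan states no figure to reproduce, so the check applies the rule to the visit schedule.

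**Inputs.** Treatment-period site visits are at days 0, 28, 56, 84 and 140, with ±2 days at Weeks 4, 8, 12 and 20 (Protocol Table 9-1). The last dose is the day before the Week 20 visit, that is day 139, and a premature-discontinuation visit also follows the last dose (Protocol 9.2.8). The treatment-emergent window is 6 × 7 = 42 days after last intake.

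**Formulas.** Imputed stop = min(15th of recorded month, last on-treatment visit, death). Let b = true stop − imputed stop, in days. On-drug days outside the window = max(0, b − 42). Post-drug days cut from the window = min(b, 42).

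**Largest b by interval**, EOT/PDV not counted, all visits attended:

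| Last visit on drug | Next visit | Latest last dose | Largest b | On-drug days lost | Same, with visit windows |
|---|---|---|---|---|---|
| Day 0 | Day 28 | Day 27 | 27 | 0 | 0 |
| Day 28 | Day 56 | Day 55 | 27 | 0 | 0 |
| Day 56 | Day 84 | Day 83 | 27 | 0 | 0 |
| Day 84 | Day 140 | Day 139 | 55 | 55 − 42 = 13 | (141 − 82) − 42 = 17 |

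Up to Week 12 the gaps are 28 days, at most 32 with visit windows, so the 42-day tail covers every on-drug day.

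**Example 1, before the recorded month.** First dose is 6 Nov 2017, the Week 12 visit is 29 Jan 2018, and the true stop is 21 Mar 2018 (day 135), recorded as March 2018.
- Imputed stop = min(15 Mar, 29 Jan) = 29 Jan, so b = 135 − 84 = 51 days.
- Duration = 84 + 1 = 85 days, against a true 135 + 1 = 136.
- The window closes on 29 Jan + 42 days = 12 Mar, instead of 21 Mar + 42 days = 2 May.
- Of the 51 days lost, 9 are on drug (13–21 Mar) and 42 are post-drug.

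**Example 2, no floor on either reading.** First dose is 20 Jan and the stop is recorded as January. Imputed stop = 15 Jan, and duration = 15 − 20 + 1 = −4 days. Likewise, a patient seen on drug on the 20th who stops later that month is imputed to the 15th.

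**Frequency among stop dates with a missing day.** The rule was applied to 365 start dates crossed with last doses on days 1–139. Equal weight for each stop day, full attendance and no deaths are assumptions.
- Site visits only: 56% of imputed dates fall before the recorded month (72% for stops after Week 12) and 12% before the last on-treatment visit. Mean b is 20 days, maximum 55. Some on-drug day is lost in 9.4% (23% for stops after Week 12).
- Week 2 and Week 19 phone contacts counted as visits: 47% before the recorded month, mean b 16 days, on-drug loss in 4.3%.
- EOT/PDV counted as on-treatment and attended 1 to 7 days after the stop: 0% before the recorded month, mean b 2 to 4 days, maximum 16, no on-drug loss.

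**The case against.** The strongest reply is that the size depends on an undefined term. Week 20 is the end-of-treatment visit, and patients who stop early should attend a discontinuation visit as soon as possible. If that visit counts as on-treatment, it is a valid upper limit and the large backdating disappears. This stands as a limit on size. It does not rescue the rule: Protocol 9.2.8 places that visit after the last dose, patients who never attend one are exposed on either reading, and the missing floor in Example 2 remains.

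A reader might infer that on-drug adverse events generally lose treatment-emergent status. The documents do not support that: the 6-week tail protects all on-drug days up to Week 12 if visits are attended. Missed visits would widen the loss.

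A reader might also infer that safety information disappears. Deaths are reclassified rather than dropped, because SAP 6.3.5 also tabulates all deaths and later ones. Individual adverse-event listings are planned (Protocol 10.3.2.4), the line for events of special interest in SAP 6.3.4 is not restricted to treatment-emergent events, and the main Kaplan-Meier analysis in SAP 6.2.3 does not use the stop date.

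Partial dates should also be few, since the last-dose time is recorded and returned drug is reconciled (Protocol 9.2.8 and 7.7). Nothing in the documents shows that vague dates cluster where a dose-related tolerability signal would appear.

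**Conclusion.** The rule is wrong as stated, not merely short of detail: it uses a lower bound as an upper bound and has no floor. Two consequences should be kept apart.

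- Dates before the recorded month, by up to 55 days on the nominal schedule, need both the last on-treatment visit in an earlier month and an EOT/PDV that is either not counted or not attended.
- Dates before a visit on drug or before the first dose occur on either reading, when that date is after the 15th of the stop month.

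The main effect is understated exposure and a post-drug window shortened by the days backdated. On-drug loss is confined to the end of the Week 12–20 gap if visits are attended. The percentages above describe stop dates with a missing day under an assumed uniform stop day; they are not proportions of trial patients. How many dates will be partial is not given, and the practical impact is probably small.

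It is tempting to extend the point to the primary result through compliance and per-protocol membership. The 6MWD test does not use the stop date directly, and the documents do not say that an imputed stop date decides who is in the per-protocol set. The correction is worth making because it is cheap and the present rule can produce impossible dates.

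**What to change.** Define the last on-treatment visit in SAP 4.3 and state that EOT/PDV is excluded. For a missing day with known month and year, impute the latest of the 15th of that month, the last on-treatment visit and the first dose date, but not after the earliest of the end of the recorded month, the EOT/PDV visit and death.

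In Example 1 this gives 15 Mar 2018 and a window to 26 Apr. In Example 2 it gives 20 Jan and a duration of 1 day. A version with the visit floor and month-end cap was run on the same grid, where first dose and baseline visit coincide; the EOT/PDV and death caps were not exercised. It gave no date outside the recorded month or before the last on-treatment visit, a mean error of about 0 days (maximum 16) and no on-drug loss.

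The cost is SAP wording and one line of derivation code, with no new data. Exposure and treatment-emergent counts become slightly higher. A latest-compatible-date rule for fully missing dates is an optional convention and not part of this correction, since no recorded month is contradicted there.
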